2.4.2 Safety endpoints

Secondary safety endpoints during 104 weeks are as follows:

- Incidence of treatment emergent AEs during 104 weeks of treatment
- Change in IGF-I from baseline during 104 weeks of treatment
- Change in HbA_{1c} from baseline to 104 weeks of treatment
- Change in clinical laboratory tests from baseline during 104 weeks of treatment
- Change in glucose tolerance (AUC of glucose and AUC of insulin) based on the OGTT from baseline to 104 weeks of treatment
- Change in bone age and bone age/chronological age from baseline to 104 weeks of treatment, and (yearly [change in bone age] / [change in chronological age]) (yearly [Δ bone age/ Δ chronological age])
- Change in vital signs (blood pressures and pulse) from baseline during 104 weeks of treatment
- Change in urinalysis from baseline during 104 weeks of treatment
- Change in blood coagulation test from baseline during 104 weeks of treatment
- Change in ECG from baseline during 104 weeks of treatment

Incidence of treatment emergent adverse events during 104 weeks of treatment

AEs will be coded using the current version of the Medical Dictionary for Regulatory Activities (MedDRA). All AEs will be presented based on system organ class and preferred terms.

A treatment emergent adverse event (TEAE) is defined as an event that has onset date on or after the date of visit 2 (0 week) and no later than the date of Visit 12 (104 weeks). For withdrawal

subjects, AEs with onset date no later than 7 days after the last day of NN-220 treatment will be included in the TEAE.

TEAEs are summarised descriptively, whereas non-treatment emergent AEs are presented in listings. TEAE data will be displayed in terms of the number of subjects with at least one event (N), the percentage of subjects with at least one event (%), the number of events (E) and the event rate per 100 years (R). Furthermore, TEAE data are summarised by seriousness, severity, relation to treatment, relation to device, withdrawal due to AEs and outcome.

Furthermore summary tables based on system organ class and preferred term are made for

- All TEAEs
- Serious TEAEs
- Possibly or probably related TEAEs
- Severe TEAEs
- Cardiac disease TEAEs
- TEAEs with preferred term that are experienced by at least 5% of the subjects in any treatment arm or by at least 5% of all subjects
- Medication errors
 - HLGTS: Medication errors, Device issues and Product Quality Issue
 - HLT: Complications associated with device NEC, Overdoses NEC, Underdoses NEC
 - PTs: Contraindicated drug administered, Drug administered to patient of inappropriate age
- Hyperglycaemia and new-onset diabetes mellitus - pre-defined MedDRA search
 - SMQ code: 20000041, narrow scope
- Malignant tumours - pre-defined MedDRA search
 - SMQ code: 20000194, narrow scope
- Central nervous system vascular
 - HLGT: Central nervous system vascular disorders
- Convulsion - pre-defined MedDRA
 - SMQ code 20000079, narrow scope
- Hyperthyroidism
 - HLT Thyroid hyperfunction disorders (MedDRA HLT code 10043740)
- Nephrotic syndrome
 - HLT Glomerulonephritis and nephrotic syndrome (MedDRA HLT code 10018365)

IGF-I

IGF-I SDS will be derived using a reference range^{vi}.

The measurements and their change from baseline during 104 weeks of treatment will be summarised descriptively.

Change in IGF-I and IGF-I SDS from baseline to 104 weeks of treatment will be analysed based on the ANCOVA model with treatment as a fixed effect and baseline as a covariate. A 95% confidence interval of the treatment difference will be provided.

HbA_{1c}

The measurements of HbA_{1c} and its change from baseline to 104 weeks of treatment will be summarised descriptively.

Clinical laboratory tests

The measurements and their change from baseline during 104 weeks of treatment will be summarised descriptively.

Glucose tolerance based on the OGTT

The measurements of glucose and insulin will be summarised descriptively.

AUC of glucose and AUC of insulin will be calculated by the usual trapezoidal. Before calculation of AUC, missing data in each individual profile with at least one valid data at screening will be imputed by mean value at each time point for all available data from all subjects. For 52 and 104 weeks, missing data in each individual profile with at least one valid data will be imputed by mean value at each time point for all available data from each treatment.

Before statistical analysis, both of AUC at baseline and at 104 weeks will be logarithmically transformed. Change in log-transformed AUC of glucose and AUC of insulin from baseline to 104 weeks will be analysed based on the ANCOVA model with treatment as a fixed effect and log-transformed baseline as a covariate. A 95% confidence interval of the treatment ratio will be provided.

Bone age

Change in bone age and bone age/chronological age from baseline to 104 weeks of treatment will be analysed based on ANCOVA model with treatment as a fixed effect and baseline as a covariate. A 95% confidence interval of the treatment difference will be provided. Yearly Δ bone age/ Δ chronological age will be summarised and graphically presented.

Vital signs (blood pressures and pulse)

The measurements and their change from baseline during 104 weeks of treatment will be summarised descriptively.

Urinalysis

The measurements and their change from baseline during 104 weeks of treatment will be summarised descriptively.

Blood coagulation

The measurements and their change from baseline during 104 weeks of treatment will be summarised descriptively.

ECCG

The measurements and their change from baseline during 104 weeks of treatment will be summarised descriptively.

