- To evaluate the growth promoting effect of NN-220 (somatropin [genetical recombination]) from baseline to 104 weeks of treatment in short stature due to Noonan syndrome.

Secondary objectives:

- To evaluate the safety profile of NN-220 from baseline to 104 weeks of treatment in short stature due to Noonan syndrome.

Endpoints:

Primary endpoint:

- Change in height SDS from baseline to 104 weeks of treatment

Key secondary endpoints:

- Incidence of treatment emergent adverse events (AEs) during 104 weeks of treatment
- Change in IGF-I from baseline to 104 weeks of treatment
- Change in HbA_{1c} from baseline to 104 weeks of treatment

Endpoints for the whole trial including the extension phase:

The period of the extension phase is 104 weeks, and the period of the whole trial will be 208 weeks [104 weeks in the pivotal phase and 104 weeks in the extension phase]. However, if the indication has not yet been approved or rejected by the PMDA at 208 weeks for the first subject, the period for the extension phase will be extended for at least 26 weeks (6 months).

The endpoints at 208 weeks for the whole trial including the extension phase are defined in the same way as for the pivotal phase.

Please refer to section [5](#) regarding the pivotal phase and the extension phase.

Trial design:

This is a multicentre, randomised, parallel-group, double-blind trial investigating the long-term efficacy and safety of two doses of NN-220 in short stature due to Noonan syndrome.

The subjects are Japanese children with Noonan syndrome where epiphyseal fusion has not taken place. The subjects are clinically diagnosed as Noonan syndrome according to van der Burgt score list. A total of 48 subjects (0.033 mg/kg/day group: 24, 0.066 mg/kg/day group: 24) will be enrolled

and randomised in this trial. NN-220 should be administered subcutaneously in a daily regimen in the upper arm, thigh, abdominal wall or gluteal region. The administration should not be repeated at the same injection site in a short period of time.

A placebo-controlled trial design has not been selected in this trial, because it is considered unethical to have children injecting placebo every day for a long period of time.

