5.4 Rationale for treatment

The route of administration and the dosage schedule for subjects randomised to NN-220 at just different doses proposed in this trial are in accordance with the Japanese labelling for other approved indications.

Many reports about GH therapy for patients with Noonan syndrome have been published^{7,8,9,10,11,12,13}. A number of studies have reported improved growth velocity in response to GH therapy, with no significant adverse effects. Recently, there has been an increasing amount of data concerning adult height in patients with Noonan syndrome treated with GH.

Japanese and overseas clinical trials investigating the effect of NN-220 on short stature in patients with Noonan syndrome are two trials of the phase 3 trial in Sweden (GHNOO-1658) and the phase 2 trial in Japan ([Table 5-2](#)).

Table 5-2 Japanese and overseas clinical trials investigating the effect of NN-220 on short stature in patients with Noonan syndrome

Reference	Patients, N (sex)	Baseline age (years)	Baseline SDS*	Dose	Therapy duration (years)	Adult height SDS*	Height gain
Clinical trials of NN-220							
Osio, 2005 (Sweden) ⁷	18 (7:M) (11:F)	8.6 (M) 7.7 (F)	-2.9 (-0.3)	0.23 mg/kg/week (N=10), 0.47 mg/kg/week (N=15) × 2 years then dose titration Estimated mean 0.35 mg/kg/week	7.5	-1.2	13 cm (M) 9.8 cm (F)
Ogawa, 2004 (Japan) ⁸	11 (7:M) (4:F)	7.5	-2.8	0.175 mg/kg/week	2	NA	NA

Results are mean values unless specified otherwise.

*: Height standard deviation score (SDS) reported according to population standards and/or (Noonan syndrome standards).

In the Japanese phase 2 trial, the change in height velocity at the investigated dose level of 0.175 mg/kg/week (0.025 mg/kg/day) was 2.2 cm/year. This is smaller compared to the change in height velocity of the approved short stature due to growth hormone deficiency at 5.2 cm/year. In addition, the result of Turner's syndrome using the previously approved dose of 0.175 mg/kg/week (0.025 mg/kg/day) was similar at 2.3 cm/year, but smaller when compared to 3.5 cm/year using the currently approved dose of 0.35 mg/kg/week (0.050 mg/kg/day). This change in height velocity of 3.5 cm/year was the same as that of short stature patients with Noonan syndrome when given a dose

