of 0.23 mg/kg/week (0.033 mg/kg/day) in a trial conducted in Sweden. Furthermore, the change in height velocity of 5.4 cm/year for short stature due to Noonan syndrome at a dose of 0.47 mg/kg/week (0.066 mg/kg/day) in Sweden was similar to that of short stature due to growth hormone deficiency at 5.2 cm/year.

Based on the above, if the same dose as the Japanese phase 2 trial is used, it would not be considered high enough to improve short stature due to Noonan syndrome, and in order to achieve the same level of efficacy in the treatment of short stature in children with Turner's syndrome at least 0.23 mg/kg/week (0.033 mg/kg/day) would be necessary, and furthermore in order to achieve the same level of efficacy as short stature due to growth hormone deficiency at least 0.47 mg/kg/week (0.066 mg/kg/day) would be necessary.

From the above reasons, the treatment method and doses for subjects in this trial have been chosen.

6 Trial population

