17.4 Secondary endpoints

17.4.1 Efficacy parameters

Efficacy parameters are as follows.

- Height velocity SDS from baseline to 52 weeks of treatment²⁸
- Height velocity SDS from 52 weeks to 104 weeks of treatment²⁸
- Height velocity from baseline to 52 weeks of treatment
- Height velocity from 52 weeks to 104 weeks of treatment

Statistical analysis

Efficacy parameters will be summarised and graphically presented.

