2.4 Secondary endpoints

2.4.1 Efficacy endpoints

Secondary efficacy endpoints are as follows.

- Height velocity SDS from baseline to 52 weeks of treatment^v
- Height velocity SDS from 52 weeks to 104 weeks of treatment
- Height velocity from baseline to 52 weeks of treatment
- Height velocity from 52 weeks to 104 weeks of treatment

Statistical analysis

Secondary efficacy endpoints will be summarised and graphically presented.

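### HbA1c, one of two continuous endpoints the protocol Summary calls key secondary, gets no between-dose estimate or confidence interval, and the height velocity endpoints are likewise only summarised by arm

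*SAP*

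**What the plan says.** Protocol section 1 (Summary) has a short list headed "Key secondary endpoints". It contains adverse event incidence, change in IGF-I and "Change in HbA_{1c} from baseline to 104 weeks of treatment".

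SAP 2.4.2 gives the HbA1c analysis in one sentence: "The measurements of HbA_{1c} and its change from baseline to 104 weeks of treatment will be summarised descriptively". Protocol 17.4.2 says the same. In the same SAP section, IGF-I, IGF-I SDS, OGTT glucose and insulin AUC, bone age and bone age/chronological age each get an ANCOVA with a treatment difference or ratio and a 95% CI.

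For height velocity and velocity SDS in each year, SAP 2.4.1 says: "Secondary efficacy endpoints will be summarised and graphically presented". Protocol 17.4.1 is equivalent: "Efficacy parameters will be summarised and graphically presented". Protocol 5.4 argues for the two doses from change in height velocity. For the lower dose: "This change in height velocity of 3.5 cm/year was the same as that of short stature patients with Noonan syndrome". For the higher dose it cites "the change in height velocity of 5.4 cm/year for short stature due to Noonan syndrome at a dose of 0.47" mg/kg/week, that is, 0.066 mg/kg/day.

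Three general rules in SAP section 2 bear on this. Treatment differences, CIs and p values are promised only for endpoints that are analysed statistically. Formal testing is confined to week 104. HbA1c, OGTT and bone age are excluded from LOCF.

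**The concern.** There is no placebo arm, so the contrast between the two doses is the only randomised comparison in the trial (protocol 5.2). An endpoint reported only as two columns of summary statistics does not use that comparison directly: nothing in the plan produces the dose difference or its uncertainty.

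For HbA1c this is hard to reconcile with its place in the Summary. The protocol states, in the rationale for exclusion criterion 3, that GH raises blood glucose, and HbA1c is the only glycaemic measure on the key list. For height velocity, the plan does not estimate between arms the kind of quantity from which the doses were argued.

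At stake is a prespecified, baseline-adjusted estimate. Without one, any dose comparison on these measures would be either a crude calculation from the tables or a post hoc model.

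**Working it through.** **1. Endpoints side by side**

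| Endpoint | On the Summary's key list? | Planned analysis at week 104 |
|---|---|---|
| Adverse event incidence | Yes | Descriptive |
| IGF-I | Yes | ANCOVA, difference, 95% CI |
| HbA1c | Yes | Descriptive |
| OGTT glucose and insulin AUC | No | ANCOVA on log scale, ratio, 95% CI |
| Bone age, bone age/chronological age | No | ANCOVA, difference, 95% CI |
| Height SDS, Noonan reference (added in SAP 2.3) | No | ANCOVA |
| Height velocity and velocity SDS, each year | No | Summaries and graphs |

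The general rule on differences and CIs does not reach HbA1c or velocity, because neither is analysed by a model. SAP section 3, which lists changes from the protocol, renames the velocity measures as secondary efficacy endpoints but leaves their analysis as it was. SAP 2.4.3 repeats the same analyses for week 208, so the omission carries over.

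Exclusion from LOCF does not explain the HbA1c choice: OGTT and bone age are excluded too, and both are modelled.

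**2. The plan's own figure**

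Protocol 17.1 uses a two-sided two-sample t-test at 5%, difference 0.45 and SD 0.5 in height SDS, and states 21 per group for 80% power. The noncentral t distribution gives 79.2% at 20 per group and 81.2% at 21, so 21 is reproduced. Allowing 10% withdrawal, 21 / 0.9 = 23.3, rounded up to 24. The sample size is not in question; it supplies the n for the next step.

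**3. Precision of the missing estimates**

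For an ANCOVA with treatment and one covariate, giving the covariate no credit for reducing variance:

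half-width = t(0.975, 2n − 3) × SD × √(2/n)

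- n = 21 per arm: 0.624 SD
- n = 24 per arm: 0.581 SD

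The documents give no SD for HbA1c change or for height velocity, so the SDs below are assumptions.

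| HbA1c SD (points) | n = 21 | n = 24 |
|---|---|---|
| 0.2 | ±0.125 | ±0.116 |
| 0.3 | ±0.187 | ±0.174 |
| 0.4 | ±0.250 | ±0.233 |

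| Velocity SD (cm/year) | n = 21 | n = 24 |
|---|---|---|
| 1.0 | ±0.62 | ±0.58 |
| 1.5 | ±0.94 | ±0.87 |
| 2.0 | ±1.25 | ±1.16 |
| 2.5 | ±1.56 | ±1.45 |

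No extra children are needed. A covariate that predicts the outcome would narrow these intervals.

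**4. Can the velocity interval be set against section 5.4?**

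The cited figures differ by 5.4 − 3.5 = 1.9 cm/year. At SD 2.0 and 21 per arm, any estimate between 1.9 − 1.25 = 0.65 and 1.25 cm/year has an interval containing both 0 and 1.9. Whether the interval could separate the two values therefore depends on an SD that the documents do not supply.

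**The case against.** The strongest reply is that the protocol and SAP agree with each other, nothing is miscalculated, and dose effects in both domains are already compared. Growth is compared by ANCOVA on height SDS (FAS and PP), by a mixed model over all post-randomisation visits, and by ANCOVA on the Noonan-reference SDS. Glucose is compared through OGTT AUC with 95% CIs, supported by a predefined search for hyperglycaemia events. By-arm means and SDs are planned at each visit, so a reader can work out a crude difference and interval. All of this stands, and it limits the consequence.

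It also stands that the word key occurs only in the Summary. Protocol 4.2.2 and 17.4.2 list HbA1c among ten safety endpoints without rank, and there is no testing hierarchy. Adverse event incidence is key and descriptive as well, so the label did not promise a model. Height velocity is not key, and OGTT AUC and bone age are secondary endpoints just as velocity is.

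What the reply leaves unanswered is narrower. Of two continuous endpoints with the same label, one is modelled and the other is not, and no reason is given.

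A reader might infer two stronger things.

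- **That the trial could say nothing about what the higher dose does to glycaemia or growth.** The analyses just listed rule that out.
- **That a velocity interval would confirm or refute the 1.9 cm/year contrast.** The documents do not support this. Section 5.4 quotes change in velocity, whereas the endpoints are on-treatment velocities. Randomisation would balance pre-treatment velocity on average, but section 5.4 does not say over which treatment period its figures were measured. The SD is unknown, and testing that contrast is not an objective.

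**Conclusion.** The concern holds in a limited form. The plan prespecifies no baseline-adjusted dose difference with a CI for HbA1c or for the height velocity endpoints. The case is stronger for HbA1c, because IGF-I, the other continuous key secondary endpoint, has exactly the analysis that HbA1c lacks. For velocity it is a reasonable supportive addition, resting on the role velocity plays in section 5.4 and not on any rank.

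The primary analysis is unaffected, and no existing result would be biased. The estimates would carry half-widths of about 0.58 SD (24 per arm) to 0.62 SD (21 per arm), or roughly ±0.12 to ±0.25 HbA1c points over an assumed SD range of 0.2 to 0.4. The multiples of SD follow from the planned numbers; the values in HbA1c points depend on the assumed SDs.

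**What to change.** **HbA1c (SAP 2.4.2).** Analyse change to week 104 by ANCOVA with treatment and baseline HbA1c, and report the dose difference with its 95% CI. State that observed week-104 data are used, since HbA1c is outside the LOCF rule.

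**Height velocity (SAP 2.4.1), optional.** Report the dose difference with 95% CI for velocity and velocity SDS in each year. Adjust cm/year velocity for age and sex and, where available, for pre-treatment velocity. The latter can be derived from the height record 40 to 64 weeks before Visit 1, which protocol 8.4.1 already designates as control data.

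**SAP section 2.** Label these as supportive estimates without multiplicity control. Amend the sentence that attaches p values to every modelled endpoint so that none is required here. Make clear that the velocity estimate for weeks 0 to 52 is not a formal test, which would otherwise conflict with the week-104-only rule. Add the changes to SAP section 3.

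The cost is a few sentences and reuse of the IGF-I code. The downside is more secondary estimates that are not multiplicity-controlled and must be read as such.

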The measurements and their change from baseline during 104 weeks of treatment will be summarised descriptively.

Change in IGF-I and IGF-I SDS from baseline to 104 weeks of treatment will be analysed based on the ANCOVA model with treatment as a fixed effect and baseline as a covariate. A 95% confidence interval of the treatment difference will be provided.

HbA_{1c}

The measurements of HbA_{1c} and its change from baseline to 104 weeks of treatment will be summarised descriptively.

Clinical laboratory tests

The measurements and their change from baseline during 104 weeks of treatment will be summarised descriptively.

Glucose tolerance based on the OGTT

The measurements of glucose and insulin will be summarised descriptively.

AUC of glucose and AUC of insulin will be calculated by the usual trapezoidal method. Before statistical analysis, both of AUC at baseline and at 104 weeks will be logarithmically transformed. Change in log-transformed AUC of glucose and AUC of insulin from baseline to 104 weeks will be analysed based on the ANCOVA model with treatment as a fixed effect and log-transformed baseline as a covariate. A 95% confidence interval of the treatment ratio will be provided.

Bone age
Change in bone age and bone age/chronological age from baseline to 104 weeks of treatment will be analysed based on ANCOVA model with treatment as a fixed effect and baseline as a covariate. A 95% confidence interval of the treatment difference will be provided. Yearly Δ bone age/ Δ chronological age will be summarised and graphically presented.

Vital signs (blood pressures and pulse)

The measurements and their change from baseline during 104 weeks of treatment will be summarised descriptively.

Urinalysis

The measurements and their change from baseline during 104 weeks of treatment will be summarised descriptively.

Blood coagulation

The measurements and their change from baseline during 104 weeks of treatment will be summarised descriptively.

ECG

The measurements and their change from baseline during 104 weeks of treatment will be summarised descriptively.

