1.2 Scope of the statistical analysis plan

This Statistical Analysis Plan (SAP) is based on the statistical analyses of GHLIQUID-4020 as planned in the trial protocol.

Changes to the statistical methods proposed in this SAP and the reason for the change must be reported in the clinical trial report (CTR).

This SAP is based on the protocol version 2.0 (Dated 03 March 2016).

2 Statistical considerations

Analyses of all efficacy endpoints will be performed based on the full analysis set (FAS). The primary analysis of the primary endpoint will be repeated on the per protocol (PP) analysis set.

Safety endpoints will be summarised using the safety analysis set (SAS).

The impact of protocol deviations and outliers may be investigated further in sensitivity analyses if deemed relevant.

Missing values for endpoints other than OGTT, HbA_{1c} and bone age will be imputed using the last observation carried forward (LOCF) method.

All endpoints will be summarised descriptively at each visit by treatment using observed data. After 104 weeks of treatment, descriptive statistics will be presented based on both observed and LOCF imputed data. Endpoints that are analysed untransformed and endpoints that are not formally analysed are summarised by the arithmetic mean, standard deviation (SD), median, and minimum and maximum value. Endpoints that are analysed log-transformed are summarised by the geometric mean, coefficient of variation (CV), median, minimum and maximum value.

LOCF imputed data will be used as the basis for plotting data.

A formal statistical test will only be performed at 104 weeks. Presentation of results from a statistical analysis will include the estimated mean treatment effects (LSMeans). Estimated mean

treatment differences (or ratios) will be presented together with two-sided 95% confidence intervals and p values for all endpoints analysed statistically.

For endpoints measured over time mean values will be plotted to explore the trajectory over time. Data collected before randomisation will only be summarised descriptively.

Statistical analysis will be performed twice, at 104 weeks and at the end of trial including extension phase.

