2.4.3 Endpoints for the whole trial including the extension phase

The period of the extension phase is 104 weeks, and the period of the whole trial will be 208 weeks [104 weeks in the pivotal phase and 104 weeks in the extension phase]. However, if the indication has not yet been approved or rejected by the PMDA at 208 weeks for the first subject, the period for the extension phase will be extended for at least 26 weeks (6 months).

The endpoints at 208 weeks for the whole trial including the extension phase are defined in the same way as for the pivotal phase.

All efficacy and safety endpoints and parameters will be summarised and analysed in the same way as for the 104 weeks.

TEAEs will be defined as an event that has onset date on or after the first day of exposure to NN-220 and no later than 7 days after the last day of NN-220 treatment.

3 Changes to the statistical analyses planned in the protocol

The following changes from the protocol are implemented in this SAP

Terminology

“Efficacy parameters” is changed to “secondary efficacy endpoints” in section 4.2 in the protocol version 2 but it is not reflected to the section 17. In this SAP, it is changed to “secondary efficacy endpoints” from “efficacy parameters”.

Exploratory analysis on the primary endpoint

In order to investigate effects of sex, age at start of treatment and baseline height SDS on the primary endpoint, change in height SDS from baseline to 104 weeks of treatment is analysed based on the ANCOVA model with treatment and sex as fixed effects and age at start of treatment and baseline height SDS as covariates.

Statistical analysis of height SDS according to the Noonan reference

A statistical analysis on change from height SDS according to the Noonan reference in the protocol is included.

Derivation of AUC

Imputation of missing data for each individual profile is specified.

Definition of treatment emergent adverse event

The date of visit 2 (0 week) instead of the first day of exposure to NN-220 is used for a definition of a treatment emergent adverse event since the first day of exposure to NN-220 is not available in the database by the end of treatment.

Treatment emergent adverse event based on pre-defined MedDRA search

Summary tables based on system organ class and preferred term are made for treatment emergent adverse event based on pre-defined MedDRA search.

4 References

-

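### Filling gaps in the 104-week OGTT with the child's own arm mean makes the confidence intervals for the glucose and insulin AUC ratios too narrow: slight for isolated gaps, larger only if many children miss several samples

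*SAP*

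**What the plan says.** Protocol 8.5.2.9 gives five OGTT samples: one before the glucose drink, then 30, 60, 90 and 120 minutes. Protocol 17.4.2 fixes only the area calculation: "AUC of glucose and AUC of insulin will be calculated by the usual trapezoidal method". The fill rule is new in the SAP, whose section 3 lists it under derivation of AUC: "Imputation of missing data for each individual profile is specified".

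The rule in SAP 2.4.2 applies to any profile with at least one valid value:

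- At screening, a missing value "will be imputed by mean value at each time point for all available data from all subjects".
- At 52 and 104 weeks, a missing value "will be imputed by mean value at each time point for all available data from each treatment".

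Change in log AUC from baseline to 104 weeks then goes into an ANCOVA with treatment and log baseline. "A 95% confidence interval of the treatment ratio will be provided", and SAP section 2 adds a p value for every endpoint analysed statistically. Section 2 also says "A formal statistical test will only be performed at 104 weeks", so the 52-week fill reaches no test. LOCF is confined to "Missing values for endpoints other than OGTT", HbA1c and bone age, so a wholly missing OGTT profile stays missing.

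The SAP sets no limit on the number of filled points, no variance correction and no AUC analysis restricted to complete profiles.

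**The concern.** A mean fill puts a child at the centre of his or her own arm. This leaves the arm difference roughly where it was but removes part of the between-child spread, while the residual degrees of freedom still count the child as fully observed. The standard error is then understated.

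Because the first sample precedes the drink, a test abandoned early keeps one valid value and has four of five points filled. The children may be as young as 3 years, so some incomplete tests are plausible.

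Protocol 6.3 justifies excluding diabetic-type children by the glucose-raising effect of growth hormone. The two AUC ratios are among the few safety endpoints with a formal dose comparison (HbA1c is only summarised). An interval that is too narrow could flag a dose difference falsely, or overstate how firmly one has been excluded.

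**Working it through.** **Sample size used.** The documents give no precision or missingness figure for the OGTT. The group size comes from Protocol 17.1: difference 0.45, SD 0.5, two-sided 5%, 80% power. The t-test formula gives n = 20.4, rounded up to the stated 21 per arm. Then 21/0.9 = 23.3 gives the stated 24. Protocol 6.1 expects 42 completers, so 21 per arm is used below.

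**How much of the AUC is filled.** The trapezoid is AUC = 15·y0 + 30·y30 + 30·y60 + 30·y90 + 15·y120. Assumed median profiles:

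- Insulin 4/40/38/30/25: 60 + 1200 + 1140 + 900 + 375 = 3675, so the fasting value supplies 60/3675 = 1.6%.
- Glucose 85/140/125/115/105: 1275 + 4200 + 3750 + 3450 + 1575 = 14250, so it supplies 1275/14250 = 8.9%.

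A child with only the fasting value is therefore almost pinned to the arm mean.

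**Hand approximation for pinned children.** Let a fraction f of each arm be pinned.

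- The estimated residual variance shrinks to about σ²(1−f), so the model SE² is about 2σ²(1−f)/n.
- Only n(1−f) children carry information, so the true variance is about 2σ²/[n(1−f)].
- The ratio of model SE to true SE is therefore about 1−f.

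With 42 − 3 = 39 degrees of freedom the critical value is 2.023, and the actual error is P(|t| > 2.023(1−f)):

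- f = 0.05: 1.922, 6.2%
- f = 0.10: 1.820, 7.6%
- f = 0.20: 1.618, 11.4%

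**Simulation of the SAP rule.** Assumptions: no dose effect, gaps completely at random at 104 weeks, log-normal profiles with the medians above, log SD 0.6 (insulin) and 0.15 (glucose), time-point correlation 0.6, between-visit factor 0.5. There were 30,000 trials per setting (Monte Carlo error about 0.13 points).

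| 104-week gaps | Type I error, insulin / glucose | Model SE ÷ true SE, insulin |
|---|---|---|
| none | 4.9% / 5.1% | 0.99 |
| 1 point in 5% of children | 5.4% / 5.2% | 0.98 |
| 1 point in 10% | 5.7% / 5.4% | 0.97 |
| 1 point in 20% | 6.5% / 5.9% | 0.94 |
| 2 points in 10% | 6.1% / 6.0% | 0.95 |
| 2 points in 20% | 7.3% / 7.2% | 0.91 |
| 4 points in 20% | 10.3% / 10.0% | 0.83 |
| fasting value only, 5% | 6.2% / 6.3% | 0.94 |
| fasting value only, 10% | 7.7% / 7.4% | 0.89 |
| fasting value only, 20% | 11.8% / 11.3% | 0.78 |

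The fasting-only rows agree with the hand approximation. Random gaps gave no bias in the ratio itself.

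**Other assumptions.** A separate simulation (CV 15% and 60%, time-point correlation 0.5 or 0.8, between-visit correlation 0.4, 3,000 trials, Monte Carlo error about 0.4 points) gave this coverage of the nominal 95% interval:

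- full data: 93.9-95.8%
- one gap in 5-10% of children: 94.0-95.0%
- two gaps in 10-20%: 92.1-94.6%
- four gaps in 20%: 89.3-90.9%

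**Screening fill alone.** With gaps only at screening and the pooled fill, type I error was 4.8%/4.9% (insulin/glucose) with two points missing in 20% of children, and the same with four. A further run gave 4.6-5.6%. Model SE over true SE was 0.99-1.00. The insulin SE rose slightly (0.1366 to 0.1399), which the model reports honestly.

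**Alternatives.** Complete-profile ANCOVA held type I error at 4.7-5.2%, and multiple imputation (20 imputations, 5,000 trials, error about 0.3 points) at 4.4-5.4%.

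**The case against.** The strongest reply is that this may never matter. No missingness rate is stated, and one missing point in 5-10% of children gives coverage that overlaps the full-data range. If the gap is the first or last sample, which the trapezoid weights by half, even 20% of children gives only 5.2-5.5%. Reaching 10-12% needs about 8 of 42 children with four of five samples missing, and nothing in the documents suggests that. All of this stands, and it is why the point is minor.

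Re-scheduling also helps. Protocol 8.1.4.2 moves non-fasting blood sampling within the visit window. Amendment 3 places the 104-week OGTT within that window, with the stated aim of clarifying when tests must be re-scheduled. A second attempt is therefore possible, although no passage says an interrupted test is repeated. SAP section 2 allows sensitivity analyses for deviations and outliers, but they are optional and imputation is not named.

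The rule is openly pre-specified, the endpoint is not among the key secondary endpoints in Protocol section 1, and it has no success criterion. Observed values are summarised separately. These facts limit the consequence but do not repair the interval.

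A reader might infer that the screening fill is equally faulty. It is not: it concerns a covariate, is pooled over arms, and leaves the test essentially intact. A reader might also infer that a 208-week interval is affected. SAP 2.4.3 says "All efficacy and safety endpoints and parameters will be summarised and analysed in the same way as for the 104 weeks", but section 2 confines formal tests to 104 weeks and the fill rule names only screening, 52 and 104 weeks. That reach is uncertain.

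**Conclusion.** The point holds for the 104-week fill. Whenever 104-week points are filled, the reported CI is too narrow and the p value too small, and nothing stated in the SAP corrects this. The inflation is negligible to small for isolated gaps and material only if many children have largely empty profiles. The sizes rest on assumed profiles, variances and correlations, 21 per arm, and gaps completely at random. The direction does not depend on the particular values chosen.

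The documents do not support a claim that the OGTT comparison will have a 10-12% error rate, or that randomly placed gaps bias the ratio. The primary endpoint and the observed-data summaries are untouched. Minor, but worth correcting because the correction is cheap.

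**What to change.** Do not base the reported 104-week CI and p value on the mean fill. Use one of these as the main analysis:

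1. **Multiple imputation.** For 104-week profiles with at least one valid value, impute missing glucose or insulin on the log scale (at least 20 imputations), conditional on arm, the screening profile and the child's own observed points. Compute AUC and ANCOVA in each completed data set and combine by Rubin's rules.
2. **Complete profiles.** Run the ANCOVA in children with complete 104-week profiles.

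In either case keep the mean fill as a sensitivity analysis and report the number of filled points by arm and time point, which shows whether the issue arose at all. The pooled screening fill can stay. Apply the change at 208 weeks only if a formal comparison is made there.

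**Cost.** SAP wording and light programming, with no new data.

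- Multiple imputation assumes missing at random. It widens the insulin SE relative to complete data by 0.3% (0.1371/0.1367, one point in 10% of children), 1.6% (0.1384/0.1362, two in 20%) or 9% (0.1497/0.1370, fasting only in 20%). These figures come from a single simulation whose imputation model matched the data-generating model, so they are a favourable case and have not been independently rerun.
- Complete-profile analysis assumes gaps completely at random. It loses about 4 of 42 children and widens the SE by 6% (0.1443/0.1365) at one point in 10%, or about 8 of 42 and 13% (0.1535/0.1363) at two points in 20%.
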